2. Proportion of patients/caregivers sufficiently understanding the key message, i.e. providing at least 75% of correct answers (Questions Q3 and Q4 of Patient/Caregiver questionnaire; at least 8 correct answers out of 10 sub-questions).
3. Proportion of patients/caregivers adequately implementing the EM, i.e. providing at least 75% of correct or appropriate answers (Questions Q6 and Q7 of Patient/Caregiver questionnaire; at least 6 correct or appropriate answers out of 8 sub-questions).

In order to allow better decision making on the eventual subsequent actions, the success rates will be evaluated separately for HCPs and patients/caregivers. The RMM will be deemed as effective based on the following definitions:

- For HCPs: if at least 2 of the 3 pertaining proportions above are equal to or above 80%
- For patients/caregivers: if at least 2 of the 3 pertaining proportions above are equal to or above 80%

Profile of HCPs with incorrect answers

The profile of HCPs with incorrect answers to the questions related to the 3 success factors will be described using all available and relevant HCPs characteristics collected in the survey (country, specialty, duration of practice, type of setting) and past experience with SULIQUA.

Profile of patients with inappropriate answers

The profile of patients with inappropriate answers to the questions related to the 3 success factors will be described using all available and relevant HCPs characteristics collected in the survey (country, treating physician's specialty, gender, age, location).

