Annex 3 Patient/caregiver survey questionnaire

**SURVEY TO EVALUATE THE KNOWLEDGE AND UNDERSTANDING OF THE KEY
SAFETY MESSAGES IN THE HEALTHCARE PROFESSIONAL GUIDE AND THE
PATIENT GUIDE FOR SULIQUA**

- Patient / Caregiver questionnaire -

SCREENER

S1. Do you - or the person you take care of - work for any pharmaceutical company or advertising/research agency? Please select one answer

1	Yes	()
2	No	()

Data: single punch
If S1=1 then THANK&CLOSE

S2. Are you - or the person you take care of - treated with Suliqua for diabetes? Please select one answer

1	Yes	()
2	No	()

Data: single punch
If S2=2 then THANK&CLOSE

S3. How long have you - or has the person you take care of - been treated with Suliqua? Please select one answer

1	Less than 3 months	()
2	From 3 to 6 months	()
3	From 7 to 12 months	()
4	More than 12 months	()

Data: single punch

S4. What kind of pen are you - or is the person you take care of - using? Please select one answer

1	Peach (Suliqua 10-40)	()
2	Green (Suliqua 30-60)	()
3	I do not know	()

Data: single punch

S5. What is your gender/ what is the gender of the person you take care of? Please select one answer

1	Female	()
2	Male	()

Data: single punch

S6. What is your age/ what is the age of the person you take care of? Please select one answer

1	< 30 years old	()
2	31- 40 years old	()
3	41- 50 years old	()
4	51- 60 years old	()
5	61- 70 years old	()
6	71-80 years old	()
7	>80 years old	()

Data: single punch

QUESTIONNAIRE

Q1. Which of the following categories of doctors do you – or does the person you take care of - see for the management of diabetes? You can select more than one answer.

1	General practice (GP) / family physician	()
2	Endocrinologist	()
3	Gastroenterologist	()
4	Diabetologist	()
5	Geriatrician	()
6	Internist /(BE, UK): Internal medicine	()
7	Diabetes specialist nurse	()
8	Other	()

Data: multiple punch

Q2. Who has trained you - or the person you take care of - on the use of Suliqua? You can select more than one answer.

1	General practitioner (GP) / family physician	()
2	Another physician, please select the specialty in the following list:	()
3	Nurse	()
4	Pharmacist	()
5	No one	()

Data: multiple punch

List: Endocrinologist, gastroenterologist, internist, geriatrician, diabetes care clinic physician

Q3. According to your knowledge, which of the following statements are true and which are false?
 Please select one answer per row.

		TRUE	FALSE

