1	The dose pointer of the pen shows the number of dose steps to be injected	()	()
2	1 dose step of Suliqua contains 1 unit of insulin glargine 100U/ml plus a corresponding amount of lixisenatide	()	()
3	Even when the needle is changed, the pen should not be used by another person	()	()
4	You cannot use a syringe to withdraw Suliqua from a pre-filled pen	()	()
5	It is important to closely monitor your blood sugar level when starting Suliqua	()	()
6	One dose step of Suliqua only states the amount of lixisenatide	()	()

Data: single punch per row

Answer: Option 6 is false.

Q4. According to your knowledge, which of the following statements are true and which are false?
 Please select one answer per row.

		TRUE	FALSE
1	The prescription should mention which pre -filled pen you should use	()	()
2	The Suliqua (10-40) pen allows a daily injection of doses between 10 and 40 dose steps	()	()
3	The Suliqua (30-60) pen allows a daily injection of doses between 30 and 60 dose steps	()	()
4	If my total daily dose is more than 60 dose steps, then I should not use any of the Suliqua pens	()	()

Data: single punch per row

If S4=1 then skip item 3

If S4=2 then skip item 2

If S4= 3 then keep item 2 and item 3

Answer: All is true

Q5. Have you - or has the person you take care of - received the Suliqua Patient Guide from your physician or pharmacist? Please select one answer

Yes No

Data: single punch

Q6. Have you - or has the person you take care of - read the following educational materials (EM) related to Suliqua before using Suliqua? Please select one answer per row.

1	Suliqua Patient Guide (information that you may have received from your physician or pharmacist)	 Yes  No
2	Patient Information Leaflet (information available in each pack of Suliqua pre-filled pen)	 Yes  No

Data: single punch per row

If Q5=2 then skip item 1

Q7. Where would you - or the person you take care of - look for additional information if you have difficulties in understanding the prescription or use of the Suliqua pen ? You can select more than one answer.

	Prescription/ missing information	
1	Ask a physician	()
2	Ask a pharmacist	()
3	Ask a nurse	()
4	Read the Information Leaflet from the Suliqua package	()
5	Read the Suliqua Patient Guide	()
6	Read on the web	()

Data: multiple punch
If Q5=2 then skip item 5

Answer: all is true

Note :

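### The patient understanding cut-off of 8 out of 10 ignores the questionnaire's skip rule: respondents who name their pen are asked 9 items, so the fixed count demands 89% where the stated criterion is 75%

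*Protocol*

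**What the plan says.** Section 9.7.1 of the protocol defines three success factors for patients and caregivers. The second, sufficient understanding, is met by a respondent "providing at least 75% of correct answers (Questions Q3 and Q4 of Patient/Caregiver questionnaire"; the same bracket then gives the working count, "at least 8 correct answers out of 10 sub-questions". The risk minimisation measure is deemed effective for patients if at least two of the three factor proportions reach 80%.

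The items are in Annex 3. Q3 has six true/false statements, the last being "One dose step of Suliqua only states the amount of lixisenatide". Q4 has four, the last being "If my total daily dose is more than 60 dose steps, then I should not use any of the Suliqua pens". Which Q4 items are shown depends on screening question S4, "What kind of pen are you - or is the person you take care of - using? Please select one answer", where 1 is the peach 10-40 pen, 2 the green 30-60 pen and 3 means the respondent does not know. The routing is:

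- "If S4=1 then skip item 3"
- "If S4=2 then skip item 2"
- "If S4= 3 then keep item 2 and item 3"

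Section 9.7.1 gives no cut-off for a respondent who is asked fewer than 10 items and does not say how an item skipped by design is scored.

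**The concern.** The count of 8 was derived from the full list of 10 items, but under the routing only respondents who cannot name the pen see the full list. For everyone else the percentage and the count in the same sentence disagree, and a respondent with 7 of 9 correct can be classified either way.

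This is one of three primary success factors for patients. If one of the other two falls short, this one decides whether the measure is called effective. The direction is also awkward. According to section 7.2, the materials are meant to prevent mix-ups between the two strengths, yet the fixed count sets the higher bar for people who know which pen they use and the lower one for people who do not.

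**Working it through.** **Inputs**

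- Percentage criterion, 75%, and count, 8 of 10: section 9.7.1.
- Q3 items, 6; Q4 items, 4; one Q4 item skipped if S4 = 1 or 2, none if S4 = 3: Annex 3.
- Decision line for the factor, 80%: section 9.7.1.
- Per-item probability of a correct answer, p: not in the protocol, so assumed and varied.

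**Reproducing the protocol's figure.** The cut-off is the smallest whole number not below 0.75 × items. With 6 + 4 = 10 items, 0.75 × 10 = 7.5, which rounds up to 8. The stated count is therefore right for 10 items, with an effective bar of 8/10 = 80%.

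**Applying the routing.** With S4 = 1 or 2 the respondent is asked 6 + 3 = 9 items, and 0.75 × 9 = 6.75 rounds up to 7.

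| Respondent | Items asked | Cut-off from 75% | Bar under that cut-off | Bar under a fixed count of 8 |
|---|---|---|---|---|
| Names a pen (S4 = 1 or 2) | 9 | 7 | 77.8% | 88.9% |
| Does not know (S4 = 3) | 10 | 8 | 80.0% | 80.0% |

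**Effect on the pass proportion.** For illustration, let the items be independent with a common probability p. The proportion passing is P(X ≥ r) for X binomial(n, p).

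| p | 8 of 9 | 7 of 9 | 8 of 10 |
|---|---|---|---|
| 0.80 | 43.6% | 73.8% | 67.8% |
| 0.85 | 59.9% | 85.9% | 82.0% |
| 0.90 | 77.5% | 94.7% | 93.0% |
| 0.95 | 92.9% | 99.2% | 98.8% |

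Solving P(X ≥ r) = 0.80 for p gives 0.907 for 8 of 9, 0.824 for 7 of 9 and 0.842 for 8 of 10. Between about 0.824 and 0.907, the choice of rule alone decides whether pen-namers reach 80%. Below that window both rules miss the line; above it both reach it.

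**Sensitivity to independence.** One person's answers are likely to be correlated. With a beta-binomial model and an assumed within-person correlation of 0.2:

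- p = 0.85: 66% pass at 8 of 9 and 79% at 7 of 9, both below the line.
- p = 0.90: 77.5% and 87%, still on opposite sides.

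**The same fault in patient factor 3.** Section 9.7.1 asks for 6 of 8 on Q6 and Q7. Q6 has 2 items and Q7 has 6. If the patient guide was not received (Q5 = No), Annex 3 skips Q6 item 1 and Q7 item 5, leaving 8 − 2 = 6 items. The fixed count then requires 6/6 = 100%, whereas 0.75 × 6 = 4.5 rounds up to 5.

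**The case against.** Several points on the other side are fair.

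- The 89% bar comes from reading the count literally. If the percentage governs and the bracket only illustrates it, 7 of 9 passes. This shows that the sentence contradicts itself for 9-item respondents; it does not show which half the analysis will follow.
- The rule for missing values in section 9.7 removes them from denominators. It can be read as allowing a 9-item denominator, but it does not mention items skipped by design or individual scores, and a fixed count of 8 would still conflict with it. The SAP could settle how skipped items are scored, but the protocol has already fixed a number that does not fit its own questionnaire.
- Rounding already lifts the bar to 80% with 10 items, so the skip itself moves it from 80% to 89%.
- Routing is certain only on the web. On paper, section 9.8.1 relies on layout to encourage skipping, so some paper respondents may answer all 10 items. This limits how exactly the 9-item figure applies, and it adds an unscored case that also touches the planned paper-versus-web comparison of success factors in section 9.7.2.
- The reversal holds only over a limited range of p and narrows when answers are correlated. The protocol does not give the share of respondents who will answer that they do not know their pen.
- Read literally, the count makes success harder, so the risk is a false negative. Failing one factor of three does not by itself fail the measure.

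These points limit the size of the effect. None of them removes the contradiction.

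**Conclusion.** The concern holds. The count of 8 is correct only for respondents who cannot name their pen. For those who can, the stated 75% means 7 of 9, and the fixed count raises the bar to 88.9%. This part rests only on section 9.7.1 and Annex 3; it is exact for web respondents and for paper respondents who follow the skips.

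The effect on the decision depends on assumptions. With independent items of equal difficulty, the rule alone decides whether pen-namers reach 80% when p lies between about 0.82 and 0.91; at p = 0.85 the gap is 86% against 60%. With correlated answers the gap is smaller and the reversal can disappear at some values of p. It matters most to the overall patient verdict when one of the other two factors has missed 80%. A primary criterion that gives two answers for the same respondent has to be corrected before any wave is scored.

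**What to change.** In section 9.7.1, define patient factor 2 as at least 75% correct of the Q3 and Q4 items applicable to the respondent: at least 7 of 9 if S4 = 1 or 2, and at least 8 of 10 if S4 = 3. State how a paper answer to an item that should have been skipped is scored; disregarding it would keep the denominator the same on web and paper.

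Word factor 3 the same way: at least 6 of 8 if the guide was received, and at least 5 of 6 if Q5 = No.

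As a sensitivity analysis for factor 2, score the 8 items put to everyone (Q3 items 1 to 6, Q4 items 1 and 4) with at least 6 of 8 required. This removes the dependence on S4, but it drops the two items on pen dose range, so it should not replace the main score.

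The cost is one sentence per factor in section 9.7.1 and matching scoring code, with no new data. Section 6 puts the end of Wave 1 collection at 30 May 2020 and the first interim report at 31 October 2020, so under that schedule the rule can be set before Wave 1 is reported and applied to all waves. If any Wave 1 scoring has been done, it can be redone from the item-level answers.

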8 RESEARCH QUESTION AND OBJECTIVES

The research questions for this study is: Were the key safety messages in the healthcare professional guide and the patient guide, implemented as risk minimisation measures (RMM) beyond routine, effective in:

- Providing a good knowledge and understanding to health care professionals (HCPs) who prescribed or dispensed SULIQUA and to patients treated with SULIQUA
- Reducing the risk of medication errors when prescribing/delivering or using SULIQUA

The main objective of this study is to assess the knowledge and understanding of the key safety messages in the healthcare professional guide and patient guide among HCPs who prescribed or dispensed SULIQUA and patients treated with SULIQUA, respectively.

Specific objectives are to assess the proportion of:

- HCPs:
 - Who receive, understand and implement the safety messages conveyed by EM for SULIQUA
 - Who are aware that prescriptions for SULIQUA should state clearly the dose range and strength of SULIQUA in a pre-filled pen and the number of dose steps to be administered by the patient
 - Who advise patients with regard to dose steps required, design, features and appropriate utilization of SULIQUA pre-filled pen, close monitoring of blood sugar levels after initiation, and anticipated adverse reactions
 - Who noted medication errors in treated patients
- Patients/caregivers
 - Who acknowledge receiving SULIQUA pre-filled pen guide for patients and caregivers
 - Who read the patient guide before using SULIQUA pre-filled pen
 - Who implemented the safe utilisation of SULIQUA according to safety information for the SULIQUA pre-filled pen
 - Who were trained/advised by their HCP (physician or pharmacist) on how to use SULIQUA pre-filled pen

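### The patient implementation factor (9.7.1) is scored mainly on how many information sources are ticked; it can be passed without reading the guide, and its two cut-offs diverge for patients who never received it.

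*Protocol*

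**What the plan says.** Section 9.7.1 defines the third patient success factor as "Proportion of patients/caregivers adequately implementing the EM, i.e. providing at least 75% of correct or appropriate answers". It draws the items from "Questions Q6 and Q7 of Patient/Caregiver questionnaire" and sets the cut-off at "at least 6 correct or appropriate answers out of 8 sub-questions". The factor is one of three; the measures are deemed effective for patients if at least two of the three proportions reach 80%.

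Annex 3 gives the items. Q6 has two yes/no rows: guide read before use, and package leaflet read before use. Q7 asks where the respondent would "look for additional information if you have difficulties in understanding the prescription or use of the Suliqua pen" and offers six boxes: physician, pharmacist, nurse, leaflet, guide, web. More than one may be ticked, and the key beneath Q7 treats all six as true. For respondents who did not receive the guide, the routing is "If Q5=2 then skip item 1" under Q6 and "If Q5=2 then skip item 5" under Q7.

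The related objective in Section 8 is the proportion of patients "Who implemented the safe utilisation of SULIQUA according to safety information for the SULIQUA pre-filled pen".

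**The concern.** Q7 asks where a patient would turn in case of difficulty. One good source is a sensible answer, and the respondent is told only that several may be chosen. The score nevertheless treats each unticked box as a lost point and gives the web the same credit as the physician or the guide. The patient guide in Annex 5 tells patients with questions to speak to their healthcare professional and does not send them to the web.

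The factor can therefore misclassify in both directions: it can fail patients who read and would use the material, and pass patients who did not read it. Because it feeds the two-of-three rule, the primary conclusion for patients can depend on it. For patients without the guide, two items disappear, and the section does not say whether the count or the percentage then governs.

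**Working it through.** **Inputs.** Cut-off of 75%, given as 6 of 8 (9.7.1). Q6 has 2 items and Q7 has 6 (Annex 3). One item in each is skipped if Q5 is No (Annex 3).

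**The plan's figure.** 2 + 6 = 8 items and 0.75 × 8 = 6, so 6 of 8 is reproduced. The arithmetic is sound; the difficulty lies in what is counted.

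**Sources needed.** Q6 gives at most 2 points, so a pass needs at least 6 − 2 = 4 of the 6 boxes in Q7.

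**Passing patterns, guide received.** There are 2^8 = 256 answer patterns. Passing: C(8,6) + C(8,7) + C(8,8) = 28 + 8 + 1 = 37. Passing with the guide unread (at least 6 of the other 7 items): 7 + 1 = 8. Passing with the guide neither read nor named as a source: 1.

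**Guide not received.** 8 − 2 = 6 items remain, giving 2^6 = 64 patterns.
- Fixed count: 6 of 6, so 1 pattern passes, and it includes the web.
- Percentage: 0.75 × 6 = 4.5, so 5 of 6. Then 6 + 1 = 7 patterns pass, one of them without the web.

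**Example patients.**

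| Patient | Q6 | Q7 | Score | Result |
|---|---|---|---|---|
| Read guide and leaflet; would ask physician, ask pharmacist, re-read guide | 2 | 3 | 5 of 8 | fails |
| Received guide but did not read it; read leaflet; ticks every source except the guide | 1 | 5 | 6 of 8 | passes |
| No guide; read leaflet; ticks physician, pharmacist, nurse, leaflet | 1 | 4 | 5 of 6 | fails on count, passes on percentage |

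**Sensitivity to tick rates.** The protocol gives none, so these are assumptions. For a recipient who read both documents, with independent ticks at a common rate p, the pass probability is P(X ≥ 4), X ~ Bin(6, p):

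| p | Passing |
|---|---|
| 0.50 | 34% |
| 0.60 | 54% |
| 0.70 | 74% |
| 0.80 | 90% |

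The 80% target is met at p of about 0.73.

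If instead every item, including the reading items, is endorsed independently with the same probability:

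| p | Recipients, 6 of 8 | No guide, 6 of 6 | No guide, 5 of 6 |
|---|---|---|---|
| 0.80 | 79.7% | 26.2% | 65.5% |
| 0.90 | 96.2% | 53.1% | 88.6% |

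**The case against.** **Unticked boxes.** The protocol never says that an unticked box is wrong. The HCP questionnaire marks certain ticks as mandatory in its prescription question; patient Q7 does not. But a total of eight sub-questions is obtained only by counting each of the six boxes, and with every option keyed true only a tick can earn the point. The inference stands.

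**Skipped items.** A reader might infer that a patient without the guide must score 6 of 6, web included. That follows only from the fixed count. The same sentence gives 75%, and Section 9.7 leaves missing values out of the denominators of proportions, which could be read as supporting 5 of 6. The protocol states neither treatment for skipped items, so what can be held against it is the divergence.

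**Inevitable failure.** A reader might also infer that the factor will fail in practice, reducing the rule to a requirement that both other factors pass. The documents do not support this: tick rates are unknown, and above about 73% the factor reaches its target among those who read both documents.

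**No link to the guide.** It would be too strong to say that the factor tells nothing about use of the guide. One Q6 row asks about reading it and one Q7 box about consulting it. They are diluted, and neither is required.

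**Direction and visibility.** A factor that is too hard to pass works against declaring success, and a patient without the guide who fails is arguably classed correctly. Section 9.7.1 also reports every answer to every question, so the components will be visible. Both points stand and soften the consequence. They do not repair the decision rule, which uses the composite, or the passes with the guide unread.

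**Conclusion.** The concern holds as a defect in a scoring rule that the protocol itself fixes. Three parts need no assumption about response behaviour: every pass needs at least four of six sources; 8 of 37 passing recipient patterns have the guide unread; and the count and the percentage disagree once two items are skipped. The pattern counts show what the rule allows, not how often it will happen.

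The effect on the 80% target is not determined. The range of 34% to 90% passing rests on independent ticks at a common rate between 50% and 80%, in patients who read both documents. The factor may pass or fail; either way the result largely reflects how many boxes respondents choose to tick. Nor do Q6 and Q7 observe safe use, which is what the Section 8 objective names.

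**What to change.** Amend 9.7.1 (and the SAP to match) before Wave 1 results are analysed:

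- Score Q7 as one item, appropriate if at least one of sources 1 to 5 is ticked. Leave the web unscored.
- Define the factor as guide read before use (Q6, row 1), leaflet read before use (Q6, row 2) and an appropriate Q7. Requiring all three fits the existing 75%, since 0.75 × 3 = 2.25 rounds up to 3.
- For the decision rule, keep all analysable patients in the denominator and count those without the guide as not implementing. This settles the skip problem.
- Show the result among guide recipients, and the 6-of-8 count, as descriptive.
- State that the factor reflects reported reading of the materials, not observed safe use.

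The decision should not rest on recipients alone. With 50% receipt and 80% of recipients qualifying, the factor would pass although only 0.50 × 0.80 = 40% of those surveyed met it, and the sample would fall below the planned 150 per wave.

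**Cost.** All items are already collected, so no new fieldwork is needed. It is a change to a primary success factor after Wave 1 collection began in September 2019 and must be declared as such. The single Q7 item will discriminate little, so the factor will rest mainly on the two reading items. The factor also cannot exceed the proportion who received the guide: if receipt is below 80%, factors 1 and 3 both fail and the two-of-three rule fails with them. That consequence should be stated and accepted in advance.
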